#### 3.2.1.2 Exclusion criteria for first randomisation

- Recipients of multi-organ transplants (eg kidney + liver, kidney + pancreas)
- previous treatment with CAMPATH;
- active infection, including HIV (antigen or antibody), hepatitis B (surface antigen), or hepatitis C (PCR) positivity;
- past history of anaphylaxis following exposure to humanised monoclonal antibodies;
- history of malignancy (with the exception of adequately treated non-melanoma skin cancer) diagnosed or recurred in the last five years;
- loss of previous kidney transplant within six months not due to technical reasons;
- medical history that might limit the individual's ability to take trial treatments for the duration of the study.

### 3.2.2 *Invitation to participate in the randomised study and patient consent*

Those patients who appear to be eligible will have the study explained to them by the study staff, using the Patient Information Sheet as a basis for discussion. Patients will be given a copy of the Patient Information Sheet and will have an opportunity to ask any questions and have a short time to think about their participation in the study. Patients will be discouraged from participating if it is thought unlikely that they would be willing and able to comply with follow-up for at least five years.

Eligible patients who agree to participate will be asked to provide written informed consent to enter the study, which will include consent for both the first and second randomisations and for long-term registry-based follow-up. One copy of the signed consent form will be filed in the patient's medical notes, one copy will be given to the patient and one copy will be stored in the site file.

### 3.2.3 *Completion of case report form*

The LCC staff will complete an electronic case report form which will include patient identifiable details (so that the patients can be "flagged" with national registries), the inclusion and exclusion criteria and basic details about their previous treatment (if any) for end-stage renal disease and the transplant itself.

### 3.2.4 *Random allocation of study treatment*

Eligible and consenting individuals will then be randomised to study treatments. The study IT system will minimise the randomisation with respect to important patient characteristics (42). The study staff will be informed which induction therapy the patient is to receive (CAMPATH- or basiliximab-based induction) and given the patient's unique study reference.

The randomisation procedure will use minimized randomisation in order to ensure that treatment groups are balanced with respect to prognostically significant variables. The minimization variables will be:

- Recipient age: ≤30, 31-59, ≥60 years old;
- Ethnicity: white, non-white;
- Type of transplant: cadaveric heart-beating donor, non-heart-beating donor, living donor;
- HLA mismatch: as per current UK Transplant protocol:
  - 0-0-0 (HLA A-B-DR) mismatch;
  - 0 DR mismatch and 0-1 B mismatch;
  - 0 DR mismatch and 2 B mismatch, or 1 DR mismatch and 0-1 B mismatch;
  - 1 DR mismatch and 2 B mismatch, or 2 DR mismatch and 0-2 B mismatch;
- patient sensitisation status: 'highly sensitized' defined, for example, by a positive cross-match with 85% of donors (reaction frequency >85%).
- centre

### 3.2.5 *Reducing dose of CAMPATH in elderly*

In view of concerns of over-immunosuppression in the elderly (and in particular the risk of post-transplant lymphoproliferative disorder in this group) the total dose of CAMPATH will be reduced in those ≥60 years old. These patients will not receive the second 30mg dose of CAMPATH.

### 3.2.6 *Informing patient's GP*

The local centre will write to inform the patient's GP of their entry into the study when they are discharged from hospital following their transplant if such information is not included in the standard discharge summary from the local hospital. The letter will include contact details for the local centre should the GP have any questions.

### **3.3 DISCHARGE VISIT**

All patients will be seen again prior to their discharge from hospital after their index admission (i.e. the admission for transplant surgery). They will ideally be seen on the day of their discharge, or as close to it as is possible.

#### *3.3.1 Further details of medical history and transplant*

Further details of the patient's medical (and in particular, renal) history will be sought and noted on the CRF. In addition, details about the transplant which would not have been available at the time of randomisation will be noted.

#### *3.3.2 Adverse events*

Any serious adverse events that occur during the index admission will be recorded on a separate SAE case report form (see section 3.10.2). This will include a description of the event (including how it meets the criteria for being a serious adverse event), the date of onset and resolution. An assessment of relationship to study treatments will also be made, and if it is thought to be related (i.e. a Suspected Serious Adverse Reaction, SSAR) then it will be reported to the Coordinating Centre immediately.

Non-serious adverse events that are thought to be related to study treatment will also be recorded at this visit.

#### *3.3.3 Discharge medication*

A list of medication (including dosages and frequency) will be recorded.

#### *3.3.4 Clinical measurements*

The patient's blood pressure, height and weight will be recorded.

#### *3.3.5 Laboratory results*

The results of blood and urine tests from the day the form is completed (or the closest available results) will be recorded. This will include serum creatinine and albumin, full blood count, tacrolimus level and urine protein:creatinine ratio.

#### *3.3.6 Health economic evaluation*

Patients will be asked to complete an EQ-5D quality of life assessment retrospectively to evaluate their quality of life prior to the admission for transplantation.

### **3.4 FOLLOW-UP VISITS (at months 1, 3, 6, 9 and 12)**

Following randomisation, patients are scheduled to be seen prior to discharge from hospital following the index admission, then at months 1, 3, 6, 9 and 12. These are timed to coincide as far as possible with the standard follow-up of these patients, so extra visits will be kept to a minimum. Telephone follow-up will be used should the patient be unable to attend a clinic follow-up.

#### *3.4.1 Adverse events*

All serious adverse events will be recorded on a separate SAE CRF. This will be similar to section 3.3.2 above. If the SAE is thought to be due to study treatment, it should be discussed immediately with the Clinical Coordinator or his/her deputy for expedited reporting (see section 3.10.3).

Non-serious adverse events should only be recorded if they are believed to be due to study treatment.

#### 3.4.2 *Current medication and clinical measurements*

The patient's current medication will be recorded. Blood pressure will be recorded at all follow-up visits and weight recorded at 6 and 12 months..

#### 3.4.3 *Blood results*

At each follow-up visit, results for creatinine and therapeutic drug level monitoring will be recorded, as well as a full blood count, lipid profile (total cholesterol, HDL-cholesterol and triglycerides if available) and urinary protein:creatinine ratio at certain visits. These will be copies of results of routine clinical tests requested by the managing team. See Appendix 6: Schedule of study procedures.

#### 3.4.4 *Health economic evaluation*

Patients will be asked to complete an EQ-5D quality of life assessment and answer a brief questionnaire to capture details of health care usage, days off work and current work status (see section 2.3.4).

#### 3.4.5 *Steroid withdrawal in basiliximab-allocated patients*

Patients allocated to basiliximab will have a reducing course of prednisolone prescribed (see Section 4.2.1.1). Prednisolone can be withdrawn completely at the discretion of the local investigator but should not be withdrawn between 5 and 7 months after surgery (i.e. around the time of the second randomisation).

### 3.5 **SECOND RANDOMISATION (at ~6 months)**

The second randomisation (between sirolimus- and tacrolimus-based maintenance therapy) can occur from 5 to 7 months post-transplantation (ideally to coincide with 6 month follow-up visit). The following exclusion criteria will apply:

- proteinuria >800 mg/day (or protein:creatinine ratio >80 mg/mmol);
- biopsy-proven acute rejection (Banff score >1) in previous month.

(See section 3.5.1 for guidance on the management of patients who are not willing and eligible for second randomisation or whose local investigator does not consider it in their best interests.)

In order to minimise the impact of this exclusion criterion, investigators will be encouraged to monitor proteinuria and treat it appropriately (with ACE inhibitors and/or angiotensin receptor blockers) during the first six months post-transplant surgery.

The second randomisation will be stratified by induction therapy allocation and minimized by prognostically-relevant criteria including graft function, proteinuria and blood pressure.

Investigators should only randomise patients for whom they remain uncertain about the benefits of CNI-based or sirolimus-based maintenance treatment. Patients with reduced graft function (e.g. eGFR <40 mL/min/1.73m^2) will not be routinely excluded, but their events in this subgroup will be monitored closely by the independent Data Monitoring Committee.

Patients will be allocated to either remain on tacrolimus (all patients to have target trough level 5-7 ng/mL) or convert to sirolimus. The target trough level for sirolimus is 6-12 ng/mL for the first six months (patients who received basiliximab induction should be maintained at the upper end of this range) and thereafter 5-10 ng/mL.

### 3.5.1 *Management of patients who do not enter maintenance therapy randomisation*

Patients who do not have their maintenance treatment randomised should have their tacrolimus target trough level reduced to 5-7 ng/mL (unless their local investigator wishes to do otherwise).

## 3.6 FOLLOW-UP AFTER ONE YEAR AFTER TRANSPLANTATION

After their one year follow-up visit, all patients will be followed-up by "flagging" with national registries (see below) and annual questionnaires (to capture information on serious adverse events, non-study medication, other health care usage, work status and a quality of life assessment). Flagging with central registries will allow long-term follow-up of all patients to reliably assess the long-term safety and efficacy of the study treatments.

### 3.6.1 *Serious adverse events*

Information about Serious Adverse Events will be collected from national registries (including but not limited to the Medical Records Information Service [MRIS], Hospital Episode Statistics, the UK Renal Registry, the Scottish Renal Registry). Further supporting documentation will be requested from the hospital where the event occurred if the SAE is:

- reported as being related to study treatment (and therefore a Suspected Serious Adverse Reaction [SSAR]; see section 3.10.1);
- a potential study endpoint (see Section 2.3).

### 3.6.2 *Laboratory results*

Relevant laboratory results will be obtained by a data feed from the Renal Registry and/or UK Transplant (or from LCC if necessary). Consent for this will have been obtained at the time of the initial surgery, and only relevant data will be requested from these sources.

### 3.6.3 *Mailed questionnaires*

All patients in the study will be sent an annual questionnaire (starting at around 2 years after transplantation) which will request details of any serious adverse events (in particular episodes of acute rejection) and current medication (including last recorded tacrolimus or sirolimus level). Questionnaires will be sent until a median follow-up of five years has occurred.

## 3.7 FOLLOW-UP AT REFERRING HOSPITALS

At certain centres it may be standard practice for patients to return to their referring hospital for routine follow-up after a certain period after transplantation. If this occurs prior to the second randomisation the investigator at the transplant centre remains responsible (after discussion with the local managing clinician) for the second randomisation and will inform the local physician of the treatment allocation. Follow-up forms will be completed by telephone by staff from the transplant centre with relevant laboratory results being sought from the local hospital.

## 3.8 DISCONTINUATION OF STUDY TREATMENT

Patients will be encouraged to adhere to study treatments during the study. However, the local investigator may decide to discontinue study treatment at any time in the interests of the patient's health and well being. For example, study treatment may be temporarily or permanently discontinued for a particular patient if one of the following criteria are met:

- **serious** adverse event **thought likely to be due to study treatment**;
- conditions or procedures in which trial agents may be contraindicated (e.g. patients on sirolimus undergoing surgery where wound healing is a concern) (see section 4.3.1.1);
- pregnancy or any other situation where, in the opinion of the patient's own doctors or the clinic staff, continuing study treatments would not be in the patient's best interest.

If a patient wishes to discontinue from study treatment, he or she would still be followed-up for the duration of the study in the usual way. Complete follow-up of such data is essential as the analysis will be on an “intention-to-treat” basis.

### 3.9 WITHDRAWAL FROM STUDY

In accordance with ICH-GCP, a patient has the right to withdraw from the study at any time and for any reason, without prejudice to his or her future medical care by the physician or at the institution, and is not obliged to give his or her reasons for doing so. If patients are no longer willing to attend study clinics or complete questionnaires, then this data will be collected directly from the transplant centre and central registries, unless patients withdraw consent for this as well.

### 3.10 REPORTING ADVERSE EVENTS

#### 3.10.1 *Non-serious adverse events*

Any non-serious adverse events that are believed to be due to study treatment will be recorded on the case report form. Other non-serious adverse events will not be recorded as they are common in this population and if not related to study treatment, analysis of such events is unlikely to yield useful information about the safety and efficacy of the study treatments.

#### 3.10.2 *Serious adverse events*

Serious adverse events (SAEs) are defined as those adverse events that:

- result in death;
- are life-threatening;
- require in-patient hospitalisation or prolongation of existing hospitalisation;
- result in persistent or significant disability or incapacity;
- are a congenital anomaly or birth defect following maternal or paternal exposure;
- are important medical events in the opinion of the responsible investigator (i.e. any event that is not immediately life-threatening and does not result in death or hospitalisation but which may jeopardise the patient or may require intervention to prevent one or the other outcomes listed above).

In addition, the following events will be recorded as Serious Adverse Events in this protocol.:

- cancers (including post-transplantation lymphoproliferative disorder)
- transplant biopsies
- rejection episodes
- loss of graft
- opportunistic infections such as cytomegalovirus and BK virus
- deliberate overdose of study treatment

All reports of SAEs will be entered on the IT system and those that are potential study endpoints will be reviewed, verified and coded (see section 3.12). SAEs that are not considered due to study treatment will be processed in a manner that allows the Coordinating Centre to provide information on such events for regulatory processes in accordance with current timelines.

---

 Such as stipulated in the European Clinical Trial Directive (Article 18 of Directive 2001/20/EC).

Information about the occurrence of study outcomes and all other serious adverse events (SAEs) will be sought at scheduled visits (for the first year after transplantation) and from national and other registries (including, but not limited to the Medical Records Information Service [MRIS], Hospital Episode Statistics, the UK Renal Registry, the Scottish Renal Registry).

The following minimum information will be collected for all SAEs:

- the unique Study Identification Number (Study ID) for the participant;
- the unique SAE Form Identification Number (SAE Form ID);
- the time and date that the SAE Form is completed;
- the source of the report (e.g. patient, relative, friend, etc.);
- a description of the event (e.g. myocardial infarction, pneumonia);
- the reason for believing the adverse event to be serious (e.g. death, life-threatening, hospitalisation, disabling, congenital anomaly in offspring, other important medical condition);
- the date the event first occurred (or started);
- the place the event was diagnosed or was managed (e.g. hospital inpatient, hospital outpatient, GP surgery, etc.);
- the number of nights spent in hospital (where appropriate);
- the name of the place the event occurred (where appropriate);
- the name of the doctor responsible for the patient's care;
- the outcome at the time of reporting (e.g. death, ongoing, recovered, unknown);
- whether believed due to study treatment, and (if so), which study treatment(s) is suspected;
- details of person reporting the SAE.

### *3.10.3 Immediate reporting of any serious adverse event believed to be due to study treatment*

All SAEs considered to be due to study treatment with a reasonable probability (i.e. Suspected Serious Adverse Reactions: SSARs) are to be reported immediately to a Coordinating Centre clinician. The Coordinating Centre clinician will then record standard information including patient study number, the identity of the person reporting the event, a narrative description of the event and the reasons for possible attribution of the event to study treatment. All such reports will be assessed promptly by the Clinical Coordinator (or his deputy) who will seek any necessary additional information, and review the event's seriousness, relatedness (preferably in discussion with the reporting party) and expectedness (see section 3.10.4). The Clinical Coordinator will provide a report of all SSARs (regardless of treatment allocation), to the Chairman of the Data Monitoring Committee at regular intervals (see section 2.6) and to the responsible Research Ethics Committee and regulatory authority in the trial Development Safety Update Report.

For those SSARs that are unexpected (Suspected Unexpected Serious Adverse Reaction, SUSAR), the Coordinating Centre will provide a report to all relevant Ethics Committees, Investigators, host NHS institution and appropriate regulatory authorities to comply with the expedited reporting requirements for SUSARs.

### *3.10.4 Expected study treatment related adverse events*

These are those defined by the documents for each study drug listed below.

---

 ideally while the patient is still with clinic staff. Failing that, it should be discussed within 12 hours of being reported.

 Such as stipulated in the European Clinical Trial Directive (Article 18 of Directive 2001/20/EC).

#### 3.10.4.1 CAMPATH

Summary of Product Characteristics dated 04 June 2009.

#### 3.10.4.2 Basiliximab

Summary of Product Characteristics dated 16 December 2008.

#### 3.10.4.3 Tacrolimus

Summary of Product Characteristics dated 26 May 2009.

#### 3.10.4.4 Sirolimus

Summary of Product Characteristics dated 14 May 2009.

### 3.11 Out-of-hours assistance

If doctors at collaborating centres have any questions, they will be able to contact an on-call doctor from the coordinating centre by calling [name] (Freefone). Such help is available 24 hours a day, seven days a week.

If patients in the study (or those considering entering the study) have any questions relating to the study, they can also call [name] (Freefone) and speak to a coordinating centre doctor.

### 3.12 CONFIRMATION AND VERIFICATION OF STUDY OUTCOMES

#### *3.12.1 Confirmation of all deaths and relevant non-fatal serious adverse events*

The LCC clinic staff will seek additional information from the hospital records and other appropriate sources about SAEs that are of particular interest. Such SAEs include those reported as acute rejection, graft loss, opportunistic infections (such as CMV and BKV), malignancy (including PTLD) or other hospital admissions.

The Coordinating Centre will also seek, from the Medical Records Information Service and other relevant sources, the certified cause of death for all patients randomised into the study. For each death reported, the LCC clinic staff will seek additional information from the hospital records and other appropriate sources.

#### *3.12.2 Central verification of study outcomes*

A Central Outcomes Adjudication Panel will review the specified causes of all deaths and all serious adverse events.

### 3.13 STUDY TREATMENTS

There are four Investigational Medicinal Products (IMPs) in the 3C study: CAMPATH and its comparator basiliximab, and sirolimus and its comparator tacrolimus. Further details of the doses used of these study treatments are given in Appendix 2: Detailed treatment schedules.

#### *3.13.1 Supply of study treatments*

All study treatments are marketed products and will be purchased by the host institution for use in the trial.

### *3.13.2 Labelling of study treatments*

Basiliximab, sirolimus and tacrolimus all have a license for renal transplantation and are used regularly as specified by this protocol. They will be prescribed by the patient's managing doctor and labelled in accordance with the requirements for a dispensed medicine. These IMPs are exempt from the labelling requirements and will be labelled according to the Clinical Trials Regulation 46(2) of SI 2004 No. 1031.

CAMPATH does not have a license for kidney transplantation but will be prescribed by the patient's managing doctor. It will be labelled by the sites according to the Medicine for Human Use (Clinical Trials) Regulation 46(1). An example label is shown in Appendix 7: Specimen label for CAMPATH.

### *3.13.3 Storage of study treatments*

A stock of CAMPATH will be stored on the transplant ward in a refrigerator and a daily temperature log kept. This stock will be labelled (with labels provided by the coordinating centre [see Appendix 7: Specimen label for CAMPATH]) and maintained by the host pharmacy to ensure that availability of CAMPATH does not limit recruitment into the study. Other study treatments will be stored according to local practice.

### *3.13.4 Modification of dose of study treatments*

The doses of study drugs to be used in the 3C study are outlined in Appendix 2: Detailed treatment schedules. However, if a patient cannot tolerate the specified dose, then it can be altered at the discretion of the local investigator. Any adverse events that lead to dose modification (or discontinuation of the study treatment) will be recorded, as will the current dose of study treatment.

### *3.13.5 Accountability of study IMPs*

CAMPATH requires a full accountability record to be maintained at the site. The other IMPs (basiliximab, tacrolimus and sirolimus) are exempt from the accountability requirements because they are being used under license on the prescription of a doctor. Furthermore, it would not be feasible to maintain such records for the duration of the study given the wide variety of routes by which participants receive such treatments around the UK.

## 4.2 Appendix 2: Detailed treatment schedules

### 4.2.1 Induction treatments:

	Day 0	Day 1	Day 2	Day 3	Day 4-	Month 6	Month 12
ALLOCATION TO CAMPATH INDUCTION							
TRANSPLANT SURGERY							
Tacrolimus				2mg bd PO	Target trough level 5-7 ng/mL	See 4.2.2	
Steroids	500mg IV methylprednisolone pre-reperfusion						
CAMPATH	30mg IV  prior to reperfusion (within 15-30 minutes of methylprednisolone)	30mg IV 24h after first dose (unless patient >60 years old)					
Other	10mg chlorphenamine IV 15-30 mins prior to CAMPATH	10mg chlorphenamine IV 15-30 mins prior to CAMPATH 1g paracetamol 30-60 mins prior to CAMPATH					
MPA	360mg pre-op PO	360mg bd PO				360mg bd PO	180mg bd PO
ALLOCATION TO BASILIXIMAB INDUCTION							
TRANSPLANT SURGERY							
Tacrolimus	0.05 - 0.1mg/kg bd PO	Target trough level 5-12 ng/mL				See 4.2.2	
Steroids	500mg IV methylprednisolone pre-reperfusion	15-20 mg pre-op PO, then reduced (see section 4.2.1.1)					
Basiliximab	20mg 1h pre-op IV				20mg IV		
MPA	540 - 720mg pre-op	540 - 720mg bd				540 - 720mg bd	540 - 720mg bd PO

 See Appendix 8 for guidelines for administration of CAMPATH

 If a centre wishes to administer CAMPATH subcutaneously they may do so in all their patients.

 If mycophenolate sodium cannot be prescribed for local reasons, a dispensation can be made to allow mycophenolate mofetil to be substituted (see Appendix 9: Mycophenolate dosing for equivalent dosing).

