##### 4.2.4.3 Dose modifications for neutropaenia

Absolute neutrophil count (x 10  /mm  )	MPA  dose			
	Year 1 Induction therapy		After year 1 Induction therapy	
	Campath	Basiliximab	Campath	Basiliximab
> 2.0	360mg bd	540-720mg bd	180mg bd	540-720mg bd
1.0 – 2.0	180mg bd	180mg bd	180mg od	180mg bd
< 1.0	stop	stop	stop	stop

This protocol does not specify any contraindicated medications, but local investigators will remain responsible for the management of the participant including all concomitant medications. The treatment schedules above are intended for guidance for the local investigator, and the detailed implementation remains their responsibility and will not be monitored by the coordinating centre.

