**Other information:**

The CAMPATH will be administered as soon as possible post-reperfusion of the transplanted organ, once patient is haemodynamically stable. In some circumstances administration may be delayed until patient is in theatre recovery.

- IV methylprednisolone 500mg will be administered intraoperatively prior to organ reperfusion.
- 15-30 minutes before administer CAMPATH give 10mg IV chlorphenamine.
- Give CAMPATH 30mg IV over 2 hours once patient is haemodynamically stable. CAMPATH infusion should be completed within 3 hours post organ reperfusion. Where the patient is unstable and the administration is delayed, CAMPATH infusion must be complete within a maximum 6 hours after organ reperfusion.

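### The protocol contradicts itself on CAMPATH dosing: the second dose is withheld either above 60 or from 60, and the first IV dose falls either before or after reperfusion

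*Protocol*

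**What the plan says.** **Age limit for the second dose.** Section 3.2.5, the section devoted to this rule, withholds the second 30 mg dose in patients aged ≥60. Its reasons are over-immunosuppression and, in particular, post-transplant lymphoproliferative disorder (PTLD). The minimisation bands in section 3.2.4 also break at 60 (31-59, then ≥60). The Day 1 cell of the Appendix 2 schedule (section 4.2.1) makes the exception only for patients >60, and section 1.7 likewise speaks of patients over 60.

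**Timing of the first IV dose.** The Day 0 cell of the same schedule places it "prior to reperfusion (within 15-30 minutes of methylprednisolone" (methylprednisolone being the 500 mg intravenous dose given before reperfusion). Footnote 7 on that row reads "See Appendix 8 for guidelines for administration of CAMPATH". Appendix 8 (section 4.8.1) then says: "The CAMPATH will be administered as soon as possible post-reperfusion of the transplanted organ, once patient is haemodynamically stable". It adds: "In some circumstances administration may be delayed until patient is in theatre recovery". The infusion is to finish within 3 hours of reperfusion, or within 6 hours at most in an unstable patient. The subcutaneous instructions (section 4.8.2) also dose after reperfusion.

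**Status of the schedule.** Section 3.13.4 refers readers to Appendix 2 for study drug doses. Section 4.2.4.3 says: "The treatment schedules above are intended for guidance for the local investigator", and that "the detailed implementation remains their responsibility and will not be monitored by the coordinating centre".

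**The concern.** Each pair of instructions is in current operative text, and a site cannot follow both members of either pair.

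The age conflict matters more. A clinician who follows the pointer in section 3.13.4 to the Appendix 2 table would give a 60-year-old the second dose that section 3.2.5 withholds on safety grounds. CAMPATH is not licensed for kidney transplantation (section 3.13.2), so there is no licensed schedule for this use to fall back on.

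On timing, someone working from the table alone would start the infusion before reperfusion and would not see the haemodynamic stability condition, which appears only in Appendix 8.

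What is at stake is consistent and safe delivery of the CAMPATH regimen across centres.

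**Working it through.** No published figure needs reproducing. The check sets the texts side by side, with a little arithmetic.

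| Item | Appendix 2 table | More specific text | Other text |
|---|---|---|---|
| Second dose withheld | >60 | ≥60 (section 3.2.5) | over 60 (section 1.7); band ≥60 (section 3.2.4) |
| First IV dose | before reperfusion | after reperfusion, patient stable (Appendix 8, IV) | after reperfusion (Appendix 8, SC) |
| Interval from methylprednisolone | 15-30 minutes | none given (Appendix 8) | – |
| Chlorphenamine before first dose | 15-30 minutes | 15-30 minutes (Appendix 8, IV) | 15-30 minutes (Appendix 8, SC) |

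**Age.**
- Under >60, a patient recorded as 60 receives 2 × 30 = 60 mg.
- Under ≥60, the same patient receives 1 × 30 = 30 mg. The ratio is 60 / 30 = 2.
- This takes age in completed years. The minimisation bands support that reading, because 31-59 followed by ≥60 leaves no gap only if age is counted in whole years.
- If over 60 instead means past the 60th birthday, the two rules differ only on the birthday itself.
- Appendix 8 does not settle the matter, since it gives no age limit for the second dose.

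**Timing.** Section 4.8.1 gives the IV dose over 2 hours.
- Latest start under the 3-hour limit: 3 − 2 = 1 hour after reperfusion.
- Latest start under the 6-hour limit (unstable patient): 6 − 2 = 4 hours after reperfusion.
- Appendix 2: a start before reperfusion.

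The two windows do not overlap.

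**Methylprednisolone interval.** The Day 0 cell contains an interval that Appendix 8 does not. The appendices do not disagree on chlorphenamine: the table's own row for other drugs matches the Appendix 8 instruction, "15-30 minutes before administer CAMPATH give 10mg IV chlorphenamine".

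**How many patients.** The protocol plans 800 patients. Assuming equal allocation, 800 / 2 = 400 receive CAMPATH, which is the ceiling for the IV timing conflict. The number is lower where footnote 8 is used: "If a centre wishes to administer CAMPATH subcutaneously they may do so in all their patients". The documents do not say how many patients will be exactly 60.

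**The case against.** The case for leaving the text alone has several parts.

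- **The table sends the reader to the fuller text.** Footnote 7 is on the CAMPATH row and points to Appendix 8, so a reader relying on the table alone is less likely for timing. This stands, but the footnote does not say that Appendix 8 overrides the cell, and it does not help with age.
- **The schedules are guidance.** Section 4.2.4.3 says so, which lowers the consequence. It does not say which page governs.
- **Controls exist.** A reader might infer from the unmonitored implementation that a second dose at 60 would go unseen. The documents do not support that. Section 2.7.2 provides monitoring visits to check conduct against the protocol, section 3.13.5 requires full CAMPATH accountability at the site, and each dose is at most one vial (section 4.8.1), so a second vial should leave a trace. The record would not show infusion timing, however, and a monitor cannot call either dose a deviation while both rules are written down.
- **No harm is shown.** A reader might infer that dosing before reperfusion is dangerous. Section 4.8.1 lists hypotension among first-dose effects, but nothing in the documents says that pre-reperfusion timing causes harm. Similarly, section 3.2.5 expresses concern about the elderly in general and does not describe a step in risk at exactly 60.

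These arguments reduce the weight of the point. They do not reconcile the texts.

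**Conclusion.** The protocol is wrong as written on both points, as an internal inconsistency of minor severity. The age conflict doubles or halves the total dose for patients aged 60 in completed years in the CAMPATH arm. This rests on the completed-years reading and nearly disappears without it. The timing conflict is a direct contradiction for the first IV dose and reaches at most about 400 patients under equal allocation. Section 3.2.5, the minimisation bands and footnote 7 suggest that ≥60 and the Appendix 8 timing are intended, but the protocol does not say so.

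A reader might go further and infer damage to the induction comparison. The documents do not support that. Neither conflict changes the sample size or power, and patients are still compared as allocated. The SAP covers only the maintenance comparison (SAP section 1) and is untouched.

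**What to change.** 1. Change the age exception in the Appendix 2 Day 1 cell and in section 1.7 to ≥60, matching section 3.2.5.
2. Amend the Appendix 2 Day 0 CAMPATH cell to the Appendix 8 timing: after reperfusion, patient stable, infusion finished within 3 hours or at most 6 hours if unstable. Delete the methylprednisolone interval from that cell. If the sponsor confirms that pre-reperfusion dosing is intended, amend Appendix 8 instead.
3. Notify sites of the governing text.

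The cost is wording in three places (two table cells and section 1.7), or in Appendix 8 in place of the Day 0 cell, plus a site notice. Sample size, data collection and analysis do not change.
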